5. **Eczema vaccinatum:** Eczema vaccinatum is a serious complication in persons with eczema and other types of chronic or exfoliative skin conditions. It can also occur among eczematous contacts of recently vaccinated persons. Vaccinial lesions (generalized papular, vesicular or pustular lesions) develop on areas of the skin that are, or had at one time been, eczematous. These areas become highly inflamed and lesions may spread to healthy skin. The rash is often accompanied by fever and individuals are systemically ill. The fatality rate for untreated cases (prior to availability of VIG) has been reported from 30-40%. Following availability of VIG, mortality was reduced to approximately 7%. Early diagnosis and prompt treatment with VIG is necessary to reduce mortality.
6. **Progressive vaccinia:** Progressive vaccinia is the most serious cutaneous complication, occurring when the local vaccination lesion fails to heal and develops progressive necrosis, with destruction of large areas of skin, subcutaneous tissue, and underlying structures. Progressive lesions may spread to other skin surfaces and to bone and viscera. Progressive vaccinia is associated with a high mortality rate. This complication has been seen in patients with a compromised immune system due to a congenital deficiency, lymphoproliferative disease, immunosuppressive treatment, or HIV infection. Management should include aggressive VIG therapy.

7. **Post-Vaccinial Encephalitis/Encephalomyelitis:** Vaccinial complications affecting the CNS are unpredictable. Post-vaccinial encephalitis typically affects children < 2 years of age and is characterized by an onset of symptoms 6-10 days following vaccination, which include seizures, hemiplegia, aphasia, and transient amnesia. Histopathological changes include generalized cerebral edema, mild lymphocytic meningeal infiltration, ganglion degenerative changes and perivascular hemorrhages. Older children and adults can develop encephalitis or encephalomyelitis characterized by an onset of symptoms 11-15 days following vaccination, which include fever, vomiting, headache, malaise, and anorexia, progressing to loss of consciousness, amnesia, confusion, disorientation, restlessness, delirium, drowsiness, seizures and coma. Histopathological changes include demyelination with lymphocytic infiltration, but limited cerebral edema. Mortality rates have ranged from 15-25%, with 25% of patients who recover being left with varying degrees and types of neurological deficits. VIG has not been shown to be effective in treating CNS disease and is not recommended. Post-vaccinial encephalitis/encephalomyelitis are diagnoses of exclusion and are not believed to be a result of replicating vaccinia virus. Although no specific therapy exists, supportive care, anticonvulsants, and intensive care might be required. A review of vaccinia-related deaths (68) during a 9-year period (1959–1966 and 1968) revealed that among first-time vaccines, 36 (52%) patients died as a result of post-vaccinial encephalitis.
8. **Fetal Vaccinia:** Fetal vaccinia is a rare, but serious complication following vaccinia vaccination during pregnancy or shortly before conception (e.g., within four weeks). To date, fewer than 50 cases have been reported and often result in fetal or neonatal death. Efficacy of VIG therapy in a viable infant or used prophylactically in women during pregnancy is unknown. The CDC has established a National Smallpox Vaccine in Pregnancy Registry. This registry will follow women during their pregnancies and their babies, after they are born, to determine the outcome of such pregnancies. The CDC can be contacted at [contact].
9. **Myocarditis/Pericarditis:** The CDC has recommended a temporary medical deferral to the voluntary Smallpox Vaccination Program for persons with heart disease or cardiovascular risk factors (March 25, 2003) and issued “interim supplementary information” regarding evidence that smallpox vaccination may cause myocarditis and/or pericarditis (March 31, 2003) in people recently vaccinated with the smallpox vaccine. The cardiac events reported include myocardial infarction, angina, myocarditis, pericarditis, and myopericarditis. Although the CDC believes that there is no evidence to conclude that the licensed vaccinia vaccine causes angina or heart attacks, it acknowledges a possible causal relationship between the vaccination and heart inflammation. The CDC continues to study the relationship, but in the meantime, recommends that individuals with underlying heart disease be excluded from participation in the current Smallpox Vaccination Program. While it is currently not possible to fully evaluate the risk of cardiac events or the risk of myocarditis, pericarditis, or myopericarditis associated with vaccinia vaccination, it is reasonable to inform patients participating in studies using recombinant vaccinia virus of these reports and provide relevant guidance for evaluating these events. Further investigation from the ongoing vaccine program may provide additional data regarding an association or lack of association with cardiovascular disease. Patients are being immunized with recombinant vaccinia vaccines with therapeutic intent and will be evaluated for cardiovascular risk factors and recent or symptomatic cardiac events per

protocol eligibility criteria. Patients will be encouraged to minimize cardiovascular disease risks and encouraged to follow risk reduction according to standard medical practice. At this time the evidence for an association with myocarditis, pericarditis, or myopericarditis seems plausible, but a rare event. If not otherwise excluded, patients with known CHF or clinically significant cardiomyopathy requiring treatment should be excluded from protocol eligibility.

Out of a total of 540,824 military personnel vaccinated with a New York City Board of Health strain of vaccinia from December 2002 through December 2003, 67 developed symptomatic myopericarditis. In the 61 ECGs that were reviewed, an identifiable abnormality was evident in 46 (75.4%). The most common abnormalities included ST-segment changes observed evident in 40 patients (65.6%); 5 patients (8.2%) had normal variant early repolarization, and T-wave abnormalities were noted in 11 patients (18.0%). In addition, cardiac enzymes were elevated in 60 of 61 (98.4%) patients evaluated with this assay. On follow-up of 64 patients, all patients had objective normalization of electrocardiography, echocardiography, graded exercise testing, laboratory testing, and functional status; 8 (13%) reported atypical, non-limiting persistent chest discomfort. Among 37,901 health care workers vaccinated with the identical strain, 21 myo/pericarditis cases were identified; 18 (86%) were revaccinees. Twelve met criteria for either myocarditis or myopericarditis, and 9 met criteria for pericarditis only (6 suspected and 3 probable). The severity of myo/pericarditis was mild, with no fatalities, although 9 patients (43%) were hospitalized.

Treatment of Vaccinia Vaccination Complications

Vaccinia Immune Globulin (VIG): First-line treatment of some of the complications of vaccinia caused by dissemination of vaccinia virus (severe cases of inadvertent inoculation involving extensive lesions or if comorbid conditions exist, severe cases of generalized vaccinia in patients that are systemically ill and whose condition might be toxic or who have serious underlying immunosuppressive illnesses, eczema vaccinatum, and progressive vaccinia) is with VIG. VIG is contraindicated, however, for the treatment of isolated vaccinia keratitis. VIG is a sterile solution of the immunoglobulin fraction of pooled plasma from individuals inoculated with vaccinia vaccine. VIG is only available through the CDC's Strategic National Pharmaceutical Stockpile by contacting the CDC's Clinician Information Line at [name] or the Director's Emergency Operations Center (DEOC) at [contact]. Upon receipt of a call from a patient or upon direct observation of a patient or contact who manifests signs and symptoms of any of the above conditions, the investigator should place a call to the CDC as soon as possible: 1) to initiate review of the clinical case, 2) to seek consultation on the appropriateness of VIG therapy, 3) to determine the appropriate VIG dose and dosing method for administration, if VIG therapy is required, and 4) to determine how to access and have the appropriate doses of VIG delivered. Early institution of VIG therapy is advised following recognition of clinical symptoms compatible with some vaccinia complications (eczema vaccinatum, severe generalized vaccinia, progressive vaccinia, and some cases of inadvertent inoculation). The effectiveness of VIG therapy appears to be time dependent. VIG has not proven to be of benefit in the treatment of post-vaccinia encephalitis, and is contraindicated for treatment of isolated vaccinia keratitis due to the increased risk of corneal scarring. A new IV formulation of VIG that has a lower level of aggregated protein allowing it to

be used by either the IM or IV route is available through the CDC. This formulation will most likely be preferred for administration and the CDC will instruct investigators regarding appropriate dosing and method of administration based on the formulation and availability. There is no guarantee that VIG will successfully treat complications. At present, there are no other anti-viral therapies of proven benefit for the treatment of vaccinia-related complications.

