2.1.2 Exclusion Criteria

- A. Immunocompromised status due to:
 - Human immunodeficiency virus (HIV) positivity.

- Active autoimmune diseases such as Addison's disease, Hashimoto's thyroiditis, systemic lupus erythematosus, Sjogren syndrome, scleroderma, myasthenia gravis, Goodpasture syndrome or active Grave's disease. Patients with a history of autoimmunity that has not required systemic immunosuppressive therapy or does not threaten vital organ function including CNS, heart, lungs, kidneys, skin, and GI tract will be allowed.
 - Other immunodeficiency diseases
- B. Chronic administration (defined as daily or every other day for continued use > 14 days) of corticosteroids deemed systemic by investigator within 28 days before the first planned dose of PSA-TRICOM. Use of inhaled steroids, nasal sprays, and topical creams for small body areas is allowed.
- C. Serious intercurrent medical illness that, in the judgment of the investigator, would interfere with patient's ability to carry out the treatment program.
- D. History of seizure, including any febrile seizure, loss of consciousness, or transient ischemic attack, or any condition that may pre-dispose to seizure (e.g., prior stroke, brain arteriovenous malformation, head trauma with loss of consciousness requiring hospitalization).
- E. Other medications used for urinary symptoms including 5-alpha reductase inhibitors (finasteride and dutasteride) and alternative medications known to alter PSA (eg phytoestrogens and saw palmetto)
- F. History of prior chemotherapy
- G. History of prior immunotherapy within the last 3 years
- H. Major surgery within 4 weeks prior to enrollment (Day 1 visit).
- I. History of allergic reactions attributed to compounds of similar chemical or biologic composition to *enzalutamide* or poxviral vaccines (e.g., vaccinia vaccine)
- J. Known allergy to eggs, egg products, aminoglycoside antibiotics (for example, gentamicin or tobramycin).
- K. History of atopic dermatitis or active skin condition (acute, chronic, exfoliative) that disrupts the epidermis
- L. Previous serious adverse reactions to smallpox vaccination
- M. Unable to avoid close contact or household contact with the following high-risk individuals for three weeks after the Day 1 vaccination: (a) children \leq 3 years of age, (b) pregnant or nursing women, (c) individuals with prior or concurrent extensive eczema or other eczemoid skin disorders, or (d) immunocompromised individuals, such as those with HIV.

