- N. Receipt of an investigational agent within 30 days (or 60 days for an antibody-based therapy) before the first planned dose of study drugs.
- O. Patients who test positive for HBV or HCV
- P. Use of herbal products that may decrease PSA levels (e.g. saw palmetto)
- Q. Any gastrointestinal disease that could hinder the absorption of enzalutamide
- R. Uncontrolled hypertension (SBP>170/ DBP>105)

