The CDC is the only source of the licensed vaccinia vaccine. The CDC will provide vaccinia vaccine to protect laboratory and other healthcare personnel, whose occupations place them at risk of exposure to vaccinia and other closely related orthopoxviruses, including vaccinia recombinants. The vaccine should be administered under the supervision of a physician selected by the study institution. Revaccination is recommended every 10 years. For instructions on obtaining the licensed vaccinia vaccine, contact Drug Services, National Center for Infectious Diseases, CDC at [contact].

Recombinant Vaccinia Vaccine Patient Care Implications, Contraindications and Potential Complications

Patient Care Implications and Contraindications

Cover vaccination sites with a sterile dry dressing (e.g., Telfa pad). Instruct patients on proper hand-hygiene, sterile dressing care, bathing, laundering of clothing, *etc.* Treat patient bandages or dressings removed from the vaccination site as infectious waste and dispose in appropriate biohazard containers. Do not administer the recombinant vaccinia vaccine if the recipient, or for at least three weeks after vaccination, their close household contacts (close household contacts are those who share housing or have close physical contact):

- have active eczema or a history of eczema or atopic dermatitis, or Darier's disease.
- have other acute, chronic, or exfoliative skin conditions (e.g., burns, impetigo, varicella zoster, severe acne, contact dermatitis, psoriasis, herpes or other open rashes or wounds), until the condition resolves.

- are pregnant or intend to become pregnant (due to the potential risk of fetal vaccinia); or are breast-feeding (due to the potential risk of contact transmission and inadvertent inoculation). It is currently unknown if vaccinia virus or antibodies are excreted in breast milk. Patients (*i.e.*, vaccinees) should avoid fathering a child for at least 4 months following completion of therapy with the recombinant vaccine.
- are in close contact with children less than 3 years of age (due to the potential risk of contact transmission and inadvertent inoculation).
- are immunodeficient or immunocompromised (by disease or therapy), including individuals with HIV infection.

Additionally, do not administer the recombinant vaccinia vaccine if the vaccinee:

- has a moderate or severe acute illness, until the illness resolves.

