- is undergoing topical steroid therapy for inflammatory eye diseases, or undergoing therapy with systemic steroids; potential immune suppression increases risk for vaccinia-related complications.
- At this time, until a more definitive causal relationship is determined, it is recommended that patients with known CHF or clinically significant cardiomyopathy, not be vaccinated with recombinant vaccinia-based vaccines, due to the potential for development of myocarditis and/or pericarditis.

Although the CDC believes that there is no evidence to conclude that the licensed vaccinia vaccine used in the Smallpox Vaccination Program causes angina or heart attacks, it acknowledges a possible causal relationship between the vaccination and heart inflammation. The CDC continues to study the relationship, but in the meantime, recommends excluding individuals with underlying heart disease from participation in the current Smallpox Vaccination Program. Patients are being immunized with recombinant vaccinia vaccines with therapeutic intent and will be evaluated for cardiovascular risk factors and recent or symptomatic cardiac events per protocol eligibility criteria. Patients will be encouraged to minimize cardiovascular disease risks and encouraged to follow risk reduction according to standard medical practice.

Due to the method of manufacturing (virus grown in primary chicken embryo dermal cells), do not administer the recombinant vaccinia vaccine to patients with a history of allergy to eggs or egg products. Do not administer the recombinant vaccinia vaccine to patients with a history of allergy or serious reaction to prior vaccinia vaccination (*e.g.*, smallpox vaccination).

Potential Complications Associated With Recombinant Vaccinia Vaccination

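### Section 11.2.6 rules out vaccinia in known CHF or clinically significant cardiomyopathy, but the eligibility lists in 2.1 name neither condition

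*Combined protocol and SAP*

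**What the plan says.** Section 11.2.6 addresses the heart in two places.

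- **Contraindications.** The list opens with "Do not administer the recombinant vaccinia vaccine if the recipient, or for at least three weeks after vaccination, their close household contacts" have certain conditions, and continues with conditions of the vaccinee himself. Within that second group it recommends that "patients with known CHF or clinically significant cardiomyopathy, not be vaccinated with recombinant vaccinia-based vaccines", because of possible myocarditis or pericarditis.
- **Myocarditis/pericarditis paragraph.** It ends with an eligibility instruction: "If not otherwise excluded, patients with known CHF or clinically significant cardiomyopathy requiring treatment should be excluded from protocol eligibility".

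Both places also say that patients "will be evaluated for cardiovascular risk factors and recent or symptomatic cardiac events per protocol eligibility criteria", which presumes that section 2.1 contains cardiac criteria.

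The nearest items in section 2.1 are generic or serve another purpose. Exclusion C covers "Serious intercurrent medical illness that, in the judgment of the investigator", would hinder the treatment programme. Exclusion D covers "loss of consciousness, or transient ischemic attack, or any condition that may pre-dispose to seizure". Exclusion R covers uncontrolled hypertension. Inclusion C requires ECOG 0–1, and inclusion J rules out life-threatening illness. Section 2.5 A requires a baseline EKG for everyone and a cardiology assessment where clinically indicated. Its stated aim is baseline function and finding men who need closer cardiac monitoring around vaccinia; it attaches no exclusion.

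**The concern.** Eligibility is confirmed against section 2.1 and a registration checklist, and eligible men are then randomised (2.3, 2.4, 3.4.1). Arm B receives the vaccinia vector on Day 1 (Appendix C), and section 11.2 describes that vector as able to replicate in mammalian cells. Any vaccinia contraindication therefore has to be caught before randomisation. If a cardiac contraindication sits only in the pharmaceutical section, a man can be declared eligible under 2.1 and assigned a vaccine that the same protocol says he should not have.

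The first stake is patient safety. There is also a smaller analytic one. If the contraindication is noticed only after assignment, an Arm B man goes without his allocated vaccine in a comparison sized at 17 evaluable men per arm. The replacement rule in 8.1.1 covers only men without a 25% PSA decline, so it does not provide for him. Setting him aside would be a post-randomisation exclusion that arises in one arm only.

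**Working it through.** The plan has no figure of its own to reproduce here. The check is a comparison of text with some simple counts.

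**Step 1. Does any criterion in 2.1 name the condition?** Inclusions A–P = 16; exclusions A–R = 18; total 16 + 18 = 34. Items naming CHF or cardiomyopathy: 0 of 34.

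**Step 2. How were the other vaccinia contraindications in 11.2.6 treated?**

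| Contraindication in 11.2.6 | Counterpart in 2.1.2 |
|---|---|
| Eczema or atopic dermatitis | K, M |
| Other skin conditions | K, M |
| Pregnancy or breast-feeding (contacts) | M |
| Close contact with young children | M |
| Immunodeficiency | A, M |
| Moderate or severe acute illness | not named; C by judgment |
| Steroid therapy | B, chronic systemic use only |
| CHF or clinically significant cardiomyopathy | not named |
| Egg allergy | J: "Known allergy to eggs, egg products, aminoglycoside antibiotics" |
| Earlier reaction to vaccinia | I, L |

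Eight of ten are carried over in whole or in part. Of the two that are not, acute illness is a temporary deferral that lasts until the illness resolves. CHF/cardiomyopathy is the only lasting contraindication without a counterpart.

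**Step 3. Would a nearby item exclude the man anyway?** Take a man with compensated, treated CHF.

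- ECOG 0–1: he can meet it.
- Inclusion J: stable disease need not be judged life-threatening.
- Exclusion C: it turns on whether the illness would interfere with carrying out treatment, by judgment. A short oral course and subcutaneous injections need not be affected.
- Exclusions D and R: they concern seizure risk and blood pressure.
- Section 2.5 A: it may bring the condition to light, but directs monitoring.

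None excludes him by rule.

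**Step 4. Do the two statements in 11.2.6 agree?** The contraindication list is not limited to treated disease. The later paragraph adds a treatment qualifier, which could attach to both conditions or to cardiomyopathy alone. On either reading the two differ in scope, at least for untreated cardiomyopathy.

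**Step 5. How many men are exposed to the gap?** With 1:1 allocation, 34 / 2 = 17 in Arm B as planned and 38 / 2 = 19 at the ceiling. The share with CHF or cardiomyopathy is not given.

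**The case against.** The strongest reply is that the exclusion already exists. The 11.2.6 sentence is protocol text, and its opening condition provides for silence elsewhere. A second barrier operates at dosing, through the do-not-administer list. A man with treated CHF may therefore satisfy 2.1 without satisfying the protocol. Vaccine is given at one centre, every man has a history, examination and EKG, and exclusion C gives authority to refuse him. Section 2.1.2 was also never a full copy of section 11: acute illness and topical eye steroids appear only there. Section 1.2.3 reports no vaccine safety concern from this trial or the phase III trial up to that point.

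Much of this stands. It makes the defect an inconsistency of placement and cross-reference, and it lowers the chance that such a man is vaccinated. It does not close the gap, because the list used to confirm eligibility is silent while 11.2.6 refers readers back to it.

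Three stronger readings are tempting and are not supported.

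- **That myocardial infarction and angina are missing too.** Section 11.2.6 does not require their exclusion here. It separates these patients, vaccinated for treatment, from the public smallpox programme and reports the CDC view that there is no evidence the licensed vaccine causes either. A new cardiac-event criterion with a time window would be a preference.
- **That a probability of enrolling such a man shows how serious this is.** Any such figure needs a prevalence that the documents lack. An assumed 1% to 5% gives 17 × 0.01 = 0.17 to 19 × 0.05 = 0.95 men in Arm B, before any safeguard. That range follows from the assumption and carries no weight for severity.
- **That the myopericarditis counts in 11.2.6 measure the harm.** They are 67 / 540,824 = 0.012% and 21 / 37,901 = 0.055%, or roughly 19 × 0.00012 = 0.002 to 19 × 0.00055 = 0.010 cases among 19 men. They come from military personnel and health care workers given smallpox vaccine, so they neither estimate nor bound the risk in CHF.

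**Conclusion.** The point holds as an internal inconsistency that should be fixed. Section 11.2.6 says that men with known CHF or clinically significant cardiomyopathy should not receive recombinant vaccinia and, at least where treatment is required, should be excluded from eligibility. None of the 34 criteria in 2.1 says so. An eligibility check against 2.1 alone could randomise such a man to Arm B.

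The size is small in numbers (17 to about 19 men in Arm B) and not quantifiable as harm. The textual finding needs no numerical assumption. The practical consequence assumes that eligibility is confirmed from 2.1 and the checklist. The checklist is not in the documents and may already carry a cardiac line. Accrual status for Cohort 1 is also not stated. The version is dated 12/5/17 and section 1.2.12.1 already reports immune data from 12 men on enzalutamide alone, so the prospective benefit may be limited.

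**What to change.** 1. Add to 2.1.2, for both arms and applied before randomisation: *Known CHF or clinically significant cardiomyopathy*. Put the same line on the registration eligibility checklist.
2. In 11.2.6, bring the myocarditis/pericarditis sentence into line with the contraindication list by removing the treatment qualifier.
3. Point the reference to protocol eligibility criteria, in both places in 11.2.6, to the new criterion and to the baseline evaluation in 2.5.
4. If accrual is closed, check the records of the 17 to 19 Arm B men for either condition.

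No new procedure is needed: history, examination and EKG with cardiology assessment are already in 2.5. The downside is the possible loss of a few otherwise eligible men. At an assumed prevalence of 1% to 5%, which the documents do not give, that is 38 × 0.01 = 0.4 to 38 × 0.05 = 1.9 of 38. Some of them would be kept out already if the 11.2.6 sentence is applied.
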